The main study assessments will be performed at baseline prior to flexible dose titration and then at the end of the fixed dose drug continuation phase. This will include: (1) patient reported measures, (2) objective measures of sleep activity, (3) neurocognitive functioning (4) assessment of associated symptoms such as fatigue, mood, and (5) quality of life. Additional assessment of patient-reported measures will be performed after dose escalation and prior to the fixed dose drug continuation. Due to practice effects and other issues related to repeated measurement, neurocognitive data will only be collected pre- and post-treatment.

Sleep diaries will be completed continuously throughout the ~10 week study. Seven-day actigraphy will be completed at each dose escalation and during the first and last weeks of fixed dose drug continuation.

Additional assessments will be performed as per the standard of care. In this population, it is standard of care for MR Brain to be performed roughly every 8-16 weeks. Data on tumor status by imaging (e.g. stable disease, imaging progression, etc) will be recorded prior to study treatment and following study treatment to assess for tumor progression as a factor contributing to changes in patient-reported and clinician assessed outcome measures.

Adverse events will be assessed every 7 days during flexible dose titration (via telephone) and at the end of the fixed dose treatment. Adverse event data will be compared to that reported in patients with narcolepsy.⁵⁰

Open Label Safety Study of Solriamfetol to Promote Wakefulness and Improve Cognition and Quality of Life in
 Patients with Primary Gliomas
 Wake Forest Baptist Comprehensive Cancer Center
 WFBCCC 98418

2. Study-Related Activities

	Pre-Study ^a ^k	Baseline Visit V1 (D1)	Begin Flexible Dose Titration (D8+1 dy)	Flexible Dose D7 (D15+1 dy)	Flexible Dose D14 (D22+1 dy)	Fixed Dose Initiation Visit V2 ^k (D29+7 dys)	End of Treatment Visit V3 (D70+7 dys)	30 day Follow Up Visit V4 ^k
Informed consent	X							
Demographics	X							
Medical history	X							
Concurrent meds	X					X	X	
Physical exam ¹		X				X	X	X
Vital signs ^b	X ^c	X				X	X	X
CBC w/diff, platelets	X					X	X	X
Serum chemistry ^d	X					X	X	X
B-HCG ^e	X							
Electrocardiogram (EKG)		X				X		
Adverse event evaluation		X	X ^f	X ^f	X ^f	X	X	X
Epworth Sleepiness Scale (ESS)	X	X ^g	X ^g	X ^g	X ^g	X ^g	X ^g	
Sleep Measures: Sleep diary, Actigraphy ^h		X ⁱ	X	X	X	X	X	

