Adverse events will be assessed by telephone call completed on D8+1 day, D15+1 day, and D22+1 day. Patients will be assessed in clinic at D29+7 days. Patients who report a symptomatic dose-limiting toxicity will de-escalate treatment back to the highest previously tolerated dose and will be seen for V2.

6. Fixed Dose Drug Continuation

At the completion of the flexible dose titration, patients will be seen for a routine study visit (V2) or via telehealth visit to document adverse events at the completion of flexible dosing, review sleep diary and actigraphy, and complete V2 assessments. Data from this interim time point may be used to clarify the trajectory of improvement, decline, and no change in study assessments. Patients will then proceed with fixed dose treatment at 300 mg p.o. once daily or the maximum tolerated dose for that patient.

Fixed dose drug continuation will be continued for 6 weeks. Patients will complete a sleep diary for the first 7 and last 7 days of fixed dose treatment; actigraphy will be collected continuously. At the completion of fixed dose treatment, patients will be seen for V3 study assessments (Section 6.7).

7. 30 Day Follow Up

All patients will be followed for 30 days following the completion of treatment to assess for delayed toxicity. Adverse events will be recorded at this 30 day follow up visit. If the patient is unable to return for this visit, adverse events will be recorded by telephone or telehealth visit.

8. Study Assessments

Assessment of sleep, neuro-cognitive function, fatigue, mood and quality of life will be assessed at baseline (V1) and at the end of the fixed-dose drug continuation phase of the study (V3). Given that patient drop out could occur during the course of the study treatment, study assessments that are not subject to significant practice and/or repeated measure effects will also be assessed after the flexible dose titration period (V2).

The following assessments will be performed:

1. Patient-reported outcome measures (PROMs) for sleep:

Changes in patient-reported outcomes measures (PROMs) are pivotal to cancer control drug approval.

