Storage Requirements: solriamfetol tablets are to be stored at room-temperature conditions, 15°C to 30°C (59°F to 86°F).

Stability: Studies are ongoing to monitor the stability of solriamfetol tablets.

12 Data Management

Informed consent document	EPIC
Protocol registration form	OnCore
Adverse Events Log (Appendix E)	OnCore
Patient Drug Diary (Appendix F)	
Fixed Dose Patient Drug Diary (Appendix G)	
Epworth Sleepiness Scale (Appendix H)	
Pittsburgh Sleep Quality Index (Appendix I)	
Brief Fatigue Inventory (Appendix J)	
Cancer Fatigue Scale (Appendix K)	
Beck's Depression Inventory (Appendix L)	
Neurocognitive Battery Form (Appendix M)	
FACT-Br (Appendix N)	
Concurrent Medication (Appendix O)	OnCore
Off-Study Form (Appendix P)	OnCore
MR Imaging Record (Appendix Q)	
Sleep Diary and Actigraphy Record (Appendix R)	
Glioma History (Appendix S)	

13 Statistical Considerations

This is a single-arm, open label, non-randomized safety study in patients with stable glioma disease. The primary outcome is safety of oral solriamfetol as doses of 75 mg daily, 150 mg daily and 300 mg daily. Secondary outcomes include ESS score, PSQI score, a composite neurocognitive battery score, FSS score, BDI score, and FACT-Br score.

1. Analysis of Primary Objective

For the primary outcome, NCI Common Terminology Criteria for Adverse Events (CTCAE) version 5.0 will be used for scoring toxicity and adverse events.

The severity and frequency of toxicity and adverse events for each dose of solriamfetol will be tabulated using descriptive statistics. The proportions of subjects who experienced grade 3 or above toxicities will be estimated, along with 95% confidence intervals by each type of toxicity.

To compare the safety of solriamfetol at 75 mg daily, 150 mg daily, 300 mg daily, chi-squared statistics will be used. If there are some cells with expected value <5 , Fisher's exact test will be used for the comparison.

2. Analysis of Secondary Objective

For the secondary outcomes, descriptive statistics will be performed for each of the outcome measures. Changes in pre- and post-treatment scores will be assessed and compared using the pair-t tests if the changes follow a normal distribution and using the Wilcoxon signed rank tests if the changes do not follow a normal distribution. For the comparison between the change in ESS score in the study patients and the published change score in patients with obstructive sleep apnea, we will use the one sample t-test for this comparison.

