Appendix T – Telephone Script

Study Number: _____ PID: _____

Investigator: [name]. Date: ____/____/____

Hello, my name is {TBD - Project Coordinator} and I am calling on behalf of {Wake Forest Baptist Medical Center}. May I please speak with {SUBJECT'S NAME}?

I am going to ask you several questions about any side effects that you have experienced in the last week. When answering these questions, I would like for you to think only about symptoms that you have had over the last 1 week. We will focus on the period of time that you have been on the current dose of the solriamfetol drug that is a part of this study.

Over the last 1 week, have you had any side effects from solriamfetol (the study drug)? Yes No

Over the last 1 week, have you had any of the following symptoms (and if so, please describe them)?

- Headache _____
- Nausea _____
- Decreased appetite _____
- Anxiety _____
- Diarrhea _____
- Dry mouth _____
- Insomnia _____
- Chest pain _____
- New shortness of breath _____
- Other _____

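### Adverse events are elicited differently at 300 mg than at 75 and 150 mg, so the Section 13.1 between-dose comparison is confounded by collection method

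*Combined protocol and SAP*

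**What the plan says.** **Schedule.** Under Sections 7.1, 7.2 and 7.5 all patients start 75 mg at about D8, after the baseline week, and step up every 7 days to 150 mg and then 300 mg unless a dose-limiting toxicity occurs. Section 7.5: "Adverse events will be assessed by telephone call completed on D8+1 day, D15+1 day, and D22+1 day. Patients will be assessed in clinic at D29+7" (the last window is also in days). Section 7.6 says that at the end of titration "patients will be seen for a routine study visit (V2) or via telehealth visit to document adverse events at the completion of flexible dosing". Section 7.1 is more general: "Adverse events will be assessed every 7 days during flexible dose titration (via telephone) and at the end of the fixed dose treatment". In the Section 7.2 table, the footnote that allows adverse events (AEs) to be assessed by telephone is attached only to D8, D15 and D22. A separate footnote allows V2 and V4 by telehealth.

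**Symptom list.** The only AE symptom list in the documents is Appendix T, the telephone script. It asks: "Over the last 1 week, have you had any of the following symptoms (and if so, please describe them"; the list is headache, nausea, decreased appetite, anxiety, diarrhea, dry mouth, insomnia, chest pain, new shortness of breath, and Other. It ties recall to dose: "We will focus on the period of time that you have been on the current dose of the solriamfetol drug". The body of the protocol does not cite Appendix T, and no list or recall window is given for V2, V3 or V4. The drug diaries (Appendices F and G) have an open side-effects column.

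**Analysis.** Section 13.1, under the primary objective: "To compare the safety of solriamfetol at 75 mg daily, 150 mg daily, 300 mg daily, chi-squared statistics will be used", with Fisher's exact test when expected counts are small. It defines no AE window per dose and makes no adjustment for exposure or mode of collection.

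**The concern.** The way patients are asked about symptoms changes at the same step as the dose. After the 75 and 150 mg weeks they are taken through a named list covering the past week. After the 300 mg week nothing says how they are asked or over what period. Seven of the nine listed symptoms are exactly those that Section 10.1 gives as the most frequent with solriamfetol, so the difference falls on the events most likely to occur.

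If prompting captures more mild events, a difference between doses, or its absence, could come from the questioning rather than the drug. Section 13.4 says the study should establish safety profiles for the three doses and supply safety data for a later randomized study. Events never elicited cannot be recovered at analysis.

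**Working it through.** **1. Which contact closes which dose (patient escalating on schedule)**

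| Contact | Period closed | Symptom list specified |
|---|---|---|
| D8 call | none; drug is just starting | Appendix T |
| D15 call | 75 mg, 1 week | Appendix T |
| D22 call | 150 mg, 1 week | Appendix T |
| V2, D29 to D36 | 300 mg, 7 to 14 days after D22 | none |
| V3, D70 to D77 | fixed dose, about 6 weeks | none |
| V4 | 30 days after treatment, off drug | none |

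No scheduled script call closes a 300 mg period.

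**2. The plan's own figures.** Section 13.4 gives detectable AE proportions of 24% (reference 10%) and 36% (reference 20%) for the doses combined. An exact one-sample binomial test with N = 36 and an upper tail of at most 0.10 reproduces both: reject at 7 or more, power 79.5%; reject at 11 or more, power 80.2%. Neither figure concerns the between-dose test, for which no power is stated.

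**3. Titration weeks only.** Inputs from Section 13.4: 36 patients at 75 mg, 33 at 150 mg, 30 at 300 mg, alpha 0.10. Assumption: unprompted capture c, relative to prompted, is 0.5 to 0.9.

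- Recorded patients = n × p × c. With a true rate of 20% at both doses, 75 mg gives 36 × 0.20 = 7.2. For 300 mg, 30 × 0.20 = 6.0 becomes 3.0 (c = 0.5) to 5.4 (c = 0.9).
- True 300 mg rate that would look like 20% = 0.20 / c: 22% (c = 0.9) to 40% (c = 0.5).
- Probability that a two-sided Fisher test at 0.10 finds 300 mg worse, true rates 15% and 40% (illustrative), 36 against 30 treated as independent as Section 13.1 implies:

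| c | Recorded 300 mg rate | Probability |
|---|---|---|
| 1.0 | 40% | 0.70 |
| 0.9 | 36% | 0.58 |
| 0.7 | 28% | 0.31 |
| 0.5 | 20% | 0.10 |

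- Three-dose chi-squared test by simulation, true rates 20/20/40%: rejection falls from about 57% at c = 1 to about 9% at c = 0.5, which is no more than the 0.10 test level.

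**4. All weeks at 300 mg counted.** Scheduled exposure is 1 week at 75 mg, 1 week at 150 mg, and up to 1 + 6 = 7 weeks at 300 mg. With a constant weekly risk w and no dose effect, the recorded 300 mg rate = [1 − (1 − w)^7] × c.

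- w = 10%, c = 0.5: 0.522 × 0.5 = 26%, against 10% at 75 mg.
- w = 20%, c = 0.5: 0.790 × 0.5 = 40%, against 20% at 75 mg.
- The chi-squared test then declares a false difference in about 55% of trials.
- The capture that exactly cancels the longer exposure is w / [1 − (1 − w)^7]: 0.17, 0.19 and 0.25 for w = 5%, 10% and 20%. All are below the assumed 0.5 to 0.9.

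**The case against.** - **Direction.** A reader might infer that the plan is biased toward showing no increase at 300 mg. The documents do not support that as a general statement. Section 13.1 sets no window, exposure at 300 mg can be seven times longer, and V2 and V3 add examination, vital signs and laboratory tests (EKG at V2) that the calls lack. This objection stands: the sign is fixed only for the titration-week contrast, and only if unprompted capture is lower.
- **Silence is not prohibition.** Nothing forbids using Appendix T at visits. Section 7.1's weekly telephone assessment can be read to include the 300 mg week, V2 may be telehealth, and the content of the AE log (Appendix E) is not visible. So it cannot be said that visits have no prompts, only that none are specified. The gap in standardisation remains.
- **Other sources.** The diaries offer dated daily side-effect entries at all doses, including 42 days in the fixed-dose form. At V2 and V3 the FACT-Br asks about nausea, headaches and treatment side effects, and the BDI about appetite and sleep. These soften the difference, and the calculation gives them no separate credit. None is a common AE list, and the questionnaires are not linked to AE recording.
- **Relevance.** The between-dose hypothesis in Section 2.1 concerns serious events such as confusion and seizures, and the confidence intervals in Section 13.1 are for grade 3 or above. Prompting matters least there. This limits the point to the listed, mostly low-grade symptoms; Section 13.1 still tabulates and compares toxicity generally.
- **Who is affected.** V4 is off drug, and de-escalated patients reach V2 and V3 on a lower dose, so those visits are not purely 300 mg contacts. This stands.

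**Conclusion.** The point holds as a problem of unequal ascertainment. Followed as written, the schedule gives scripted one-week questioning after 75 and 150 mg and unspecified questioning after 300 mg, within a comparison that belongs to the primary analysis.

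The size cannot be fixed from the documents. On the assumed 50 to 90% capture, the titration-week contrast could hide a true 300 mg rate of up to 40% behind a recorded 20%. If all 300 mg weeks are pooled, a false increase is the likelier error over that same capture range. Two opposing, unmeasured distortions do not cancel by design; they leave either result hard to interpret for the common symptoms. Conclusions about serious or grade 3 and higher events are much less affected. The change is worth making because it is cheap now and impossible after data collection.

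**What to change.** 1. Give the Appendix T checklist at V2 and V3, and at V4 for delayed toxicity, as well as in the calls. Use it in person or by telehealth, before open questioning, and retitle it as the AE checklist for all contacts.
2. At V2, record onset dates and take a separate answer for the first 7 days on 300 mg, because the visit may fall up to 14 days after the step.
3. State in Section 13.1 that the between-dose comparison of these symptoms uses only the first-7-day checklist answer at each dose, with V3 and V4 answers tabulated separately.

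Step 3 is essential. If checklist answers from later weeks at 300 mg were pooled in, two checklist weeks against one would give 1 − 0.8² = 36% against 20% at a constant 20% weekly risk, a false dose effect.

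The cost is a few minutes at visits that already take place, an appendix title and a sentence in Section 13.1. More mild events will be recorded.

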This is a single-arm, open label, two-part safety study of solriamfetol in patients with WHO grade 2-4 gliomas. Patients with stable disease by clinical examination and neuroimaging who have an ESS \geq 10 and meet all inclusion/exclusion criteria will be recruited and enrolled. First, all patients will receive solriamfetol at escalating doses. Second, all patients will complete a fixed dose drug continuation treatment at the patient-specific maximum tolerated dose.

The study will occur in 3 phases:

Open Label Safety Study of Solriamfetol to Promote Wakefulness and Improve Cognition and Quality of Life in
Patients with Primary Gliomas
Wake Forest Baptist Comprehensive Cancer Center
WFBCCC 98418

1. Pre-Treatment Baseline (~1 week)
2. Flexible Dose Titration (~3 weeks)
3. Fixed Dose Drug Continuation (~6 weeks)

Patients will initially complete a 1-week baseline actigraphy and sleep diary prior to treatment initiation to establish a baseline sleep pattern.

Solriamfetol will be dosed by flexible dose titration starting at 75 mg daily in all patients and escalating after 7 days (1 week) to 150 mg daily and then after 7 days to 300 mg daily for a total duration of 3 weeks (flexible dose titration period). Patients who experience a dose-limiting toxicity will be de-escalated to the last tolerated dose level and move to the fixed dose drug continuation phase. Prior studies incorporating this design have used a 3-day treatment prior to escalation.⁴⁹ For this study, 7 days has been selected to provide a sufficient period of time to observe both immediate and delayed toxicities that could be seen in this population.

Following completion of the flexible dose titration, patients will continue solriamfetol at 300 mg daily or their maximally tolerated dose for a treatment duration of 6 weeks. For this period of the study, 8 weeks has been selected to allow for time to observe both short term improvement in patient-reported sleep as well as potentially more delayed changes in other study endpoints (i.e. fatigue, mood, neurocognition).

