Based on our prior cross-sectional study, we anticipate 30% of patients to be enrolled during adjuvant therapy (i.e. receiving oral chemotherapy), 30% during post-adjuvant surveillance (i.e. not receiving any prescribed antitumor therapy), and approximately 30% during post-recurrent disease treatment (i.e. undergoing salvage treatment with chemotherapy). This will allow for comparisons of toxicity, tolerability, and activity by timing during cancer care.

We anticipate that approximately 20-30% of patients will be taking active corticosteroids and 60% of patients will be prescribed an antiepileptic agent. This will allow us to explore differences in tolerability and activity by these important treatment parameters.

Screening assessments may be completed by telehealth visit. These will be done through MWH when able. If not able, Doximity will be used which is what is done clinically for these patients.

4. Pre-Treatment Baseline

All patients who complete written informed consent and meet eligibility criteria will be registered and will proceed with study treatment. For patients who complete consent at the time of a regularly scheduled visit they can be provided with a baseline sleep diary and actigraph device to complete the Pre-Treatment sleep diary and actigraphy prior to Visit 1 (V1). For patients who elect to take consider study enrollment and return at a later date, sleep diary and actigraphy can be completed after (in the first 7 days after) Visit 1 (V1).

Enrolled patients will complete the pre-treatment study assessments (Section 6.7). Patients will be instructed to complete a 1-week pre-treatment baseline assessment with 7-day sleep diary that records time in bed, time awake, and estimated hours of sleep among other items (Appendix Q) as well as 7-day actigraphy (see Section 7.8.2).

Patients will either return to clinic or receive a telephone call from the study nurse, study coordinator, or study team at the end of this pre-treatment baseline week (Day 7+1 day) to record the completion of pre-treatment baseline actigraphy and sleep diary.

Baseline visit will be performed in-person.

5. Flexible Dosing Titration

Upon completion of pre-treatment baseline assessments, patients will begin flexible dosing titration. All patients will begin solriamfetol 75 mg p.o. once daily. The dose will be titrated every

7 days (+1 day) to 150 mg daily and then 300 mg daily unless the patient experiences symptomatic dose-limiting toxicity.

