To assess fatigue, the Brief Fatigue Inventory (BFI) and Cancer Fatigue Scale (CFS) will be used (Appendix J & K). The BFI is a 9 item self-administered patient-reported questionnaire exploring the severity of fatigue and interference on life over the past 24 hours.⁵⁹⁻⁶¹ The Cancer Fatigue Scale is a 15-item self-administered patient-reported questionnaire exploring both overall and domain specific fatigue in cancer patients. The instrument explores three fatigue domains: physical effects of fatigue, cognitive effects, and affective issues related to cancer fatigue.⁶² The combination of these instruments provides both a unidimensional (BFI) and multidimensional (CFS) assessment of fatigue. The CFS domains will allow us to also explore whether there might be differential effects on physical fatigue or cognitive aspects of fatigue compared to the affective factors. The BFI and CFS have robust psychometric properties, have been validated in cancer patients, and were recently reviewed in the American Society of Clinical Oncology Patient-Reported Outcomes (PRO) Recommendations.^{42,43,60}

To assess depression, the Beck's Depression Inventory will be used (Appendix L). The BDI is a commonly employed measure of depressive symptoms and has been validated in cancer patients.^{63,64} A cutoff of BDI \geq 10 is often employed.⁶⁵

These measures will be completed at V1, V2, and V3 (see 7.2 Study-Related Activities).

5. Quality of Life:

The Functional Assessment of Cancer Therapy (FACT) questionnaires are commonly used to assess cancer-related quality of life (Appendix N). The FACT-Brain (FACT-Br) provides an additional set of disease-specific questions pertaining to brain neoplasms and is commonly used in brain tumor studies to evaluate disease-specific quality of life.⁶⁵

The FACT-Br will be assessed at V1, V2, V3 (see 7.2 Study-Related Activities).

9. Treatment Administration

Treatment will be administered on an outpatient basis. The study drug is to be taken orally once daily at approximately the same time each day. Each dose administered is to be recorded in the drug diary (Appendix F-G).

Reported adverse events and potential risks are described in Section 10.0. Appropriate dose modifications for are described in Section 8.0.

1. Definition of Dose-Limiting Toxicity (DLT)

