A DLT is defined as a clinically-significant AE or abnormal laboratory value assessed as unrelated to disease progression, intercurrent illness, or concomitant medications and which meets any of the criteria below. Based on the prior studies of solriamfetol in patients with narcolepsy and obstructive sleep apnea, treatment is anticipated to be safe at all doses. In the prior phase 2a study, no patient had to discontinue the study treatment due to a treatment-related DLT.⁴⁷ In the prior phase 2b study, in patients who experienced an AE requiring discontinuation of solriamfetol, the AEs were not deemed to be related to the study medication. In the prior phase 3 study, 9 patients (9%) including one in the 75 mg arm, 3 in the 150 mg arm, and 5 in the 300 mg arm required discontinuation due to treatment related AEs.⁴⁵

In prior studies, common adverse events include that have not required dose medication include headache (9-16%), nausea (12-14%), diarrhea (11%), decreased appetite (6-14%), anxiety (6-11%), chest discomfort (9%), insomnia (6%), muscle tightness (6%), nasopharyngitis (5-14%), and dry mouth (5-10%).

For this study, treatment-related DLTs are defined below. Dose limiting toxicities must have an attribution of possible, probable, or definite to solriamfetol. For patients experiencing a DLT during the dose escalation period, solriamfetol will be held. If the patient recovers (\leq grade 1 [or tolerable grade 2 for non-hematologic toxicity] or \leq baseline), a dose reduction (1 dose level reduction) is required. The patient will proceed with 7-days of drug treatment at the new dose level and reassessed. If there is no evidence of AE then the patient will proceed to the fixed dose drug continuation phase of the study at that dose.

If there is any question or clarification required concerning a potential DLT, the treating clinician should contact the Study Chair to determine the patient's DLT status. The Study Chair will make the final decision.

- **Hematological toxicities** are not expected with this agent, must NOT be attributed to another source, and will be considered dose limiting only if any of the following occur and are probably or definitely attributed to solriamfetol:
 - ANC of < 500/mm³
 - Platelets < 25,000/mm³
 - Febrile neutropenia
- Note: Grade 3 or 4 lymphopenia will not be considered a DLT.
- **Central nervous system toxicities** will be considered dose limiting only if any of the following occur:

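### Section 7.5 stops dose escalation for a symptomatic DLT, whereas 7.1, 7.9.1 and Section 8 act on any DLT, including a symptom-free laboratory value

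*Combined protocol and SAP*

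**What the plan says.** The dosing rule for the titration weeks appears in four places.

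- **Section 7.5, escalation rule.** The dose goes up every 7 days to 150 mg and then 300 mg "unless the patient experiences symptomatic dose-limiting toxicity".
- **Section 7.5, after the list of telephone contacts.** "Patients who report a symptomatic dose-limiting toxicity will de-escalate treatment back to the highest previously tolerated dose", and such patients are then seen for V2.
- **Section 7.1.** "Patients who experience a dose-limiting toxicity will be de-escalated to the last tolerated dose level". There is no reference to symptoms.
- **Section 7.9.1.** "A DLT is defined as a clinically-significant AE or abnormal laboratory value", subject to exclusions for disease, intercurrent illness and other medication. The action is also stated without a symptom condition: "For patients experiencing a DLT during the dose escalation period, solriamfetol will be held", and on recovery "a dose reduction (1 dose level reduction) is required". A DLT at 75 mg, the lowest level, ends treatment.
- **Section 8.** Dose changes in the titration period follow the DLT scheme, cited as Section 6.9.1. Section 7.9 sends the reader to Section 8 for dose modifications.

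The term symptomatic DLT is not defined anywhere in the protocol.

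**The concern.** The qualifier matters only if a DLT can occur without symptoms, and 7.9.1 allows that. Its haematological criteria include an ANC below 500/mm³ and "Platelets < 25,000/mm³", neither of which requires fever, bleeding or any complaint. Section 7.5 is an operative dosing instruction, so a literal reading of its escalation clause gives more drug to a patient for whom 7.9.1 requires less or none. In a study whose primary outcome is safety by dose, the stopping rule should read the same wherever it is stated. What is at stake is the handling of an individual patient, not an estimate or a test.

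**Working it through.** The protocol has no figure to reproduce here. The check compares the rule texts and then traces the dose each one gives.

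**Step 1. Trigger in each place.**

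| Place | Trigger | Symptom qualifier |
|---|---|---|
| 7.5, escalation clause | symptomatic DLT | yes |
| 7.5, sentence after the telephone schedule | reported symptomatic DLT | yes |
| 7.1 | DLT | no |
| 7.9.1, action during escalation | DLT | no |
| 7.9.1, closing rule under the dose table | DLT | no |
| Section 8, titration | the DLT scheme, by reference | no |

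**Step 2. Can a DLT be symptom-free under 7.9.1?** Yes, on three grounds.

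- The definition names abnormal laboratory values alongside adverse events. The neutrophil and platelet thresholds stand alone, with febrile neutropenia as a separate item.
- Grade 3 and 4 non-haematological, non-CNS toxicities are dose limiting unless excepted. A symptom-free Grade 3 electrolyte change is excepted only if it reverses within 3 days and does not come back, so other symptom-free electrolyte changes can still qualify. AST and ALT elevations are not on the exception list.
- Where the authors wanted symptoms to count, they said so, as with CNS haemorrhage.

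**Step 3. Dose under each rule.** Dose levels are 75, 150 and 300 mg (7.9.1). Take a patient with a clinically significant, attributable, symptom-free laboratory DLT.

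| DLT found during | 7.5 escalation clause, read literally | 7.9.1 |
|---|---|---|
| 75 mg week | next level: 150 mg | discontinue: 0 mg |
| 150 mg week | next level: 300 mg | hold, then on recovery one level down: 75 mg |

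In the second row the doses differ by 300 / 75 = 4-fold. That is a ratio of dose levels for one hypothetical patient, not an effect size. Two escalation steps are affected (75 to 150, and 150 to 300). In the 300 mg week there is no further step, so the clause has nothing to raise.

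**Step 4. How would such a DLT come to light?** The schedule in 7.2 places blood counts and chemistry at pre-study, V2, V3 and the 30-day follow-up, with none between first dose and V2. The titration contacts may be made by telephone, and the script in Appendix T asks about side effects and symptoms. A laboratory DLT in the first two dose weeks would therefore have to come from an unscheduled test. Section 7.3 expects about 30% of patients on adjuvant chemotherapy and about 30% on salvage chemotherapy. Such patients may well have other blood tests, but the documents do not say how often.

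**Step 5. What else must hold?** Haematological DLTs are described as not expected, must not be attributed to another source, and need probable or definite attribution to solriamfetol. Other DLTs need at least possible attribution. The documents give no laboratory DLT rate, so no patient count can be derived.

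**The case against.** The strongest case is that this is loose summary wording beside a controlling section. Section 8 is the dose-modification section, expressly covers titration and defers to the DLT scheme; 7.9 points there ("Appropriate dose modifications for are described in Section 8.0"); and the Study Chair settles doubts about DLT status. A careful reader would probably follow 7.9.1. That stands, and it keeps the point small. It does not remove the conflict: no text ranks 7.9.1 above 7.5, Section 8 cites a Section 6.9.1 that does not exist (Section 6 ends at 6.3), and the Chair's ruling that an event is a DLT leaves two different actions on the page.

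A second argument is that the de-escalation sentence directly follows the telephone schedule, and on a call a patient can report only symptoms. This also stands. A reader might infer that 7.5 twice confines the rule to symptomatic events and so exempts all others from de-escalation. The sentence does not say that: it states what happens to one group and nothing about the rest. The conflict rests on the escalation clause, which comes before any mention of telephone calls and is worded as a condition.

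A third argument is that the case is nearly empty for blood counts. In patients on chemotherapy another cause is readily available, and 7.9.1 then rules the event out as a DLT. This is fair for neutrophils and platelets. It is weaker for non-haematological laboratory toxicities, where possible attribution is enough.

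**Conclusion.** The contradiction is real and minor. The escalation clause in 7.5, read literally, raises the dose at two steps where 7.9.1 stops treatment (DLT at 75 mg) or holds and reduces it (DLT at 150 mg). The second use of the word in 7.5 is inconsistent wording only.

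The conclusion assumes a clinically significant laboratory DLT without symptoms, attributed to solriamfetol as 7.9.1 requires, and found on an unscheduled test in the 75 or 150 mg week. That combination should be rare.

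A reader might infer that patients will in practice be escalated through laboratory toxicity, or that the safety comparison by dose is compromised. The documents support neither: they give no rate for such events, 7.9.1 would probably be followed, and no analysis or sample-size figure depends on the word. Nothing here concerns V2 or the fixed-dose phase.

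**What to change.** Amend the two sentences in 7.5:

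- Delete *symptomatic* in both.
- Add *as defined and managed in Section 7.9.1 (including discontinuation for a DLT at 75 mg)*. The parenthesis is needed because 75 mg is the starting dose, so there is no previously tolerated dose to return to.
- In the second sentence change *report* to *have*, so that the rule does not depend on how the event came to light.
- Keep the instruction that these patients are seen for V2. Section 7.9.1 does not mention that visit, so replacing the sentence with a bare cross-reference would lose it. V2 carries the examination, vital signs, blood tests and EKG.

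As a clerical matter, correct the two references in Section 8 from 6.9.1 to 7.9.1 in the same amendment.

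The cost is a few words, with no added tests, visits or patients.
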